6.2.8. Physical Examination and Vital Signs

Physical examination will include a review of all body systems and measurement of weight, per each Investigators standard practice. Physical examination findings will be documented in the subject's source documents.

Vital signs include measurement of blood pressure, pulse, respiratory rate, and body temperature. Vital signs are to be measured with the subject in a sitting position after 5 minutes.

Any physical examination finding or vital sign measurement that represents a worsening from Baseline condition and is considered by the Investigator to be clinically significant will be recorded as an AE (see Section 7).

6.2.9. 12-Lead Electrocardiogram

A 12-lead ECG will be performed during Screening using validated machinery available locally to each clinical site. ECG parameters to be captured include heart rate (bpm), PR interval, QRS duration, QT interval, corrected QT interval (using Fridericia's formula), and RR interval Each report will be reviewed

by the Investigator or qualified sub-investigator and assessed as normal, abnormal – not clinically significant, or abnormal – clinically significant. Abnormal, clinically significant findings are to be reported as part of the subject's medical history.

6.2.10. Clinical Laboratory Assessments

Blood samples will be collected at the time points specified in Table 6-1 for assessment of routine chemistry and hematology analytes. Additional blood samples will be collected for coagulation studies at the time points specified in Table 6-1.

All samples will be analyzed via a central laboratory.

Table 6-2: Clinical Laboratory Analytes

Serum	Chemistry
Serum	Chemistry

- Albumin
- Alkaline phosphatase
- ALT
- AST
- Bilirubin (total and direct)
- Glucose
- Blood urea nitrogen
- Calcium
- Bicarbonate/Carbon Dioxide
- Chloride
- Total cholesterol
- Triglycerides
- Creatinine
- Gamma-glutamyl transferase
- Lactate dehydrogenase
- Phosphate
- Potassium
- Sodium
- Total protein
- Uric acid

Hematology

- Differential (absolute and percent)
- Basophils
- Eosinophils
- Lymphocytes
- Monocytes
- Neutrophils
- Erythrocytes
- Mean corpuscular hemoglobin
- Mean corpuscular hemoglobin concentration
- Mean corpuscular volume
- Hemoglobin
- Leukocytes
- Platelets

Coagulation Studies

- Prothrombin time
- Partial thromboplastin time
- INR

Clinical laboratory findings that represent a worsening from Baseline value and are considered by the Investigator to be clinically significant will be recorded as an AE (refer to Section 7).

6.2.11. Pharmacokinetics (PK)

Blood samples for PK are to be collected at the timepoints specified in Table 6-1. The actual sample collection time on the designated visit days is per study center / subject convenience. The actual sample collection date and time relative to the most recent study drug dose is to be documented.

6.2.12. Biomarker Testing

Plasma samples for protein biomarker assessment are to be collected at the timepoints specified in Table 6-1. At Screening all subjects will only have the A β 42/40 plasma ratio assessed from these samples. Subsequent samples will be stored for future protein biomarker testing once applicable assays are identified or developed; note that such samples will be not be used for genetic testing.

For purposes of use during analysis of the clinical results, biomarker status (positive/negative) will be determined by historical amyloid PET, if available. If prior amyloid PET is not available, then biomarker status is to be determined by historical biomarker testing in CSF. If prior CSF is not available, then biomarker status is to be determined by Screening Aβ42/40 plasma ratio.

6.2.13. Withdrawal of Subjects

A subject may be discontinued from study treatment at any time if the subject, the Investigator, or the Sponsor feels that it is not in the subject's best interest to continue. The following is a list of possible reasons for study treatment discontinuation:

- Subject withdrawal of consent (or withdrawal of surrogate consent)
- Subject develops suicidal ideations or attempts suicide
- Subject is not compliant with study procedures
- AE that in the opinion of the Investigator would be in the best interest of the subject to discontinue study treatment
- Protocol violation requiring discontinuation of study treatment
- Lost to follow-up
- Sponsor request for early termination of study

If a subject is withdrawn from treatment due to an AE, the subject will be followed and treated by the Investigator until the abnormal parameter or symptom has resolved or stabilized.

A subject may be withdrawn from the study at any time if the subject, the Investigator, or the Sponsor feels that it is not in the subject's best interest to continue.

All subjects are free to withdraw from participation at any time, for any reason, specified or unspecified, and without prejudice.

Reasonable attempts will be made by the Investigator to provide a reason for subject withdrawals. The reason for the subject's withdrawal from the study will be specified in the subject's source documents.

Refer to Table 6-1 for assessments to be performed for subjects who prematurely discontinue study drug.

7. ADVERSE EVENTS AND SERIOUS ADVERSE EVENTS/SAFETY REPORTING

The Investigator is responsible for reporting of events meeting the criteria and definition of an AE or SAE as provided in this protocol.

7.1. Definitions and Criteria

7.1.1. Adverse Events

Per International Council for Harmonisation (ICH) E2A: An AE is any untoward medical occurrence in a patient or clinical investigation subject administered a pharmaceutical product and which does not necessarily have to have a causal relationship with this treatment. An AE can therefore be any unfavorable and unintended sign (including an abnormal laboratory finding, for example), symptom, or disease temporally associated with the use of a medicinal product, whether or not considered related to the medicinal product.

Medical interventions such as surgeries, diagnostic procedures, and therapeutic procedures are not AEs but the action taken to treat the medical condition. They should be recorded as treatment of the AEs.

7.1.2. Serious Adverse Events

An SAE or reaction is any untoward medical occurrence that at any dose:

- Results in death
- Is life-threatening
- Requires inpatient hospitalization or prolongation of existing hospitalization
- Results in persistent or significant disability or incapacity
- Is a congenital anomaly or birth defect
- Is an important medical event (e.g., intensive treatment in an emergency room or at home for allergic bronchospasm; blood dyscrasias, or convulsions that do not result in hospitalization; or development of drug dependency or drug abuse; malignancy)

Note: The term "life-threatening" in the definition of "serious" refers to an event in which the subject was at risk of death at the time of the event; it does not refer to an event that hypothetically might have caused death if it were more severe.

Medical and scientific judgement should be exercised in deciding whether expedited reporting is appropriate in other situations, such as important medical events that may not be immediately life-threatening or result in death or hospitalization, but may jeopardize the subject or may require intervention to prevent one of the other outcomes listed in the definition above. These should also usually be considered serious.

Examples of such events are intensive treatment in an emergency room or at home for allergic bronchospasm; blood dyscrasias, or convulsions that do not result in hospitalization; or development of drug dependency or drug abuse.

Seriousness (not severity) serves as a guide for defining regulatory reporting obligations. An SAE is not necessarily severe; e.g., an overnight hospitalization for a diagnostic procedure must be reported as an SAE even though the occurrence is not medically serious. By the same token, a severe AE is not necessarily serious: nausea of several hours' duration may be rated as severe but may not be considered serious.

The following hospitalizations are not considered serious:

- A visit to the emergency room or other hospital department <24 hours, that does not result in admission (unless considered 'important medical event' or event life-threatening).
- Elective surgery, planned prior to signing the informed consent form (ICF).
- Medical/surgical admission for purpose other than remedying ill health state and was planned prior to entry into the study.
- Admission encountered for another life circumstance that carries no bearing on health status and requires no medical/surgical intervention (e.g., lack of housing, economic inadequacy, care-giver respite, family circumstances, administrative).

7.1.3. Unexpected Adverse Drug Reactions

An unexpected adverse drug reaction (ADR) is a reaction for which the nature or severity is not consistent with the applicable product information (Investigator's Brochure, Package Insert for marketed products). Until product information is amended, expedited reporting is required for additional occurrences of the reaction. Reports that add significant information on specificity or severity of a known, already documented SAE constitute unexpected events. For example, an event more specific or more severe than described in the Investigator's Brochure would be considered "unexpected." Specific examples would be (a) acute renal failure as a labeled ADR with a subsequent new report of interstitial nephritis and (b) hepatitis with a first report of fulminant hepatitis.

Guidance on reporting AEs and SAEs is described in Section 7.2.

7.1.4. Abnormal Laboratory Values

Any abnormality in a laboratory value that is new in onset or which has worsened in severity or frequency from the baseline condition and meets 1 of the following criteria will be recorded on the AE pages of the eCRF:

- Requires therapeutic intervention or diagnostic tests.
- Leads to discontinuation of investigational product.
- Has accompanying or inducing symptoms or signs.
- Is judged by the Investigator as clinically significant.

7.1.5. Assessing Intensity and Relationship

All AEs will be assessed on 2 descriptive parameters: intensity and relationship to the investigational product:

Intensity refers to the severity of an event and references impact on a subject's functioning.

• Relationship refers to the likelihood that the event being assessed was caused by the investigational product.

Intensity

Each AE will be classified according to the following criteria:

Mild: The AE does not interfere in a significant manner with the subject's normal level of

functioning.

Moderate: The AE produces some impairment of functioning, but is not hazardous to the

subject's health.

Severe: The AE produces significant impairment of functioning or incapacitation and is a

definite hazard to the subject's health.

When changes in the intensity of an AE occur more frequently than once a day, the maximum intensity for the experience should be noted. If the intensity category changes over a number of days, those changes should be recorded separately (with distinct onset dates).

Relationship

Each AE will be assessed as to its relationship to the investigational product, based on the following criteria. Although the attribution by the Investigator will be collected for reported events, for analytic purposes a temporal association with the use of the investigational product will be assumed sufficient for at least plausible association.

Not related: No causal relationship exists between the investigational product and the AE, but an

obvious alternative cause exists, e.g., the subject's underlying medical condition or

concomitant therapy.

Possibly related: A connection with the administration of the investigational product appears unlikely,

but cannot be ruled out with certainty. An AE may be considered possibly related if or when it meets 2 of the following criteria: (1) it follows a reasonable temporal sequence from administration of the investigational product; (2) it could not readily have been produced by the subject's clinical state, environmental or toxic factors, or other modes of therapy administered to the subject; or (3) it follows a known pattern

of response to the investigational product.

Related: There is a reasonable/plausible possibility that the AE may have been caused by the

investigational product.

When assessing the relationship to the investigational product, the following criteria will be considered:

- Positive rechallenge
- Positive dechallenge (resolution upon stopping suspect the investigational product, in absence of other intervention or treatment)
- Known class effect
- Biological plausibility
- Lack of alternative explanation—concomitant drug or disease

7.2. Reporting Procedures and Requirements

7.2.1. Adverse Events (AE)

AEs occurring from when the subject signs the ICF until the last study event will be recorded. Any AEs occurring before the start of treatment (i.e., before the first dose of the investigational product)" will be recorded in the medical history. Also, the sign, symptom, or disease present before starting the treatment period are only considered AEs if they worsen after starting the treatment period.

If the Investigator detects an AE in a study subject after the last scheduled follow-up visit and considers the event possibly related or related to prior study treatment, the Investigator should report it to Worldwide Clinical Trials.

The Investigator should report all AEs on the AE page(s) of the eCRF and source documents, regardless of seriousness, severity, and causality. Whenever possible, an AE will be reported using a diagnostic term rather than symptoms, (e.g., "common cold" or "upper respiratory infection" rather than "runny nose, cough, mild fever") and should be described with the attributes described in Section 7.1.5.

7.2.2. Serious Adverse Events (SAE)

Each AE will be assessed to determine whether it meets seriousness criteria (Section 7.1.2). If the AE is considered serious, the Investigator should report this event to Worldwide Clinical Trials outlined below and also to the IEC according to its standard operating procedures.

The Investigator must report all SAEs via an eCRF in the EDC system within 24 hours of learning about the event regardless of relationship to study drug.

If the Investigator/site experiences a temporary disruption of the EDC system, a back-up paper SAE Report Form will be available for Investigator/site staff to complete. If a paper SAE Report Form is utilized, it must follow the same timelines and be emailed or faxed within 24 hours of learning about the event regardless of relationship to study drug.

SAE Reporting:

E-mail: [contact]

[contact] (US) or [contact] (ROW)

If notification is made via email or fax, site staff must enter the SAE information into the EDC system as soon as the system becomes available. Should a paper SAE form be used, the original SAE form should be kept at the site.

Each SAE should be followed up until resolution or stabilization. For reported deaths, the Investigator should supply Worldwide Clinical Trials and the IEC with any additional requested information (e.g., autopsy reports and terminal medical reports).

The Sponsor or designee is responsible for notifying the relevant regulatory authorities of certain events. It is the Investigator's responsibility to notify the IEC of all SAEs that occur at the Investigator's site. Investigators will also be notified of all unexpected, serious, drug-related events (7/15 Day Safety Reports) that occur during the clinical trial.

SAEs that are ongoing at the Follow-up visit should be followed until resolution, until the condition stabilizes, until the subject is lost to follow-up or otherwise explained.

If the Investigator detects an SAE in a study subject after the last scheduled follow-up visit, and considers the SAE related or possibly related to prior study treatment, the Investigator should report it to the Sponsor.

8. DATA MANAGEMENT AND STATISTICAL ANALYSIS

8.1. Data Management and Quality Assurance Considerations

This study will employ eCRFs via an electronic data capture (EDC) system. The site will be trained on specific forms and procedures for source documentation and maintenance of an audit trail of the data that is entered on the eCRF prior to study initiation.

Study personnel at each site will enter data from source documents corresponding to a subject's visit into the protocol-specific eCRF when the information corresponding to that visit is available. Subjects will not be identified by name in the study database or on any study documents to be collected by the Sponsor (or designee), but will be identified by subject number (6 digits: the first 3 for the study center and the last 3 for the subject).

The Investigators will prepare and maintain adequate and accurate source documents designed to record all observations and other pertinent data for each subject treated with the study drug.

If a correction is required for an eCRF, the time and date will be automatically recorded by the EDC system indicating the person updating eCRF data in order to create an audit trail. The Investigator is responsible for all information collected on subjects enrolled in this study. All data collected during the course of this study must be reviewed and verified for completeness and accuracy by the Investigator.

Queries will be issued for any inconsistencies, omissions, and discrepancies and will be resolved by the appropriate parties.

Database lock will occur once quality assurance procedures have been completed.

The statistical analysis of this data will be performed by the Sponsor or designee. All AEs will be coded using the latest version of the Medical Dictionary for Regulated Activities (MedDRA). Concomitant medications will be coded using the latest version of the World Health Organization Drug Dictionary.

All procedures for the handling and analysis of data will be conducted using good computing practices meeting United States Food and Drug Administration (FDA), European Medicines Agency, and ICH guidelines for the handling and analysis of data for clinical studies. Data management details will be outlined in a separate Data Management Plan.

8.2. Sample Size

A total of approximately 80 subjects are planned to be enrolled, of whom 40 are planned to receive neflamapimod and 40 are planned to receive placebo.

As there is no prior experience with neflamapimod in patients with DLB upon which to base assumptions of treatment effect, no formal sample size calculation has been performed. However, based on prior experience with NTB in clinical studies, 40 subjects per treatment arm should provide a reasonably robust first assessment of whether neflamapimod improves cognitive function in patients with DLB.

8.3. Analysis Sets

The safety analysis set will include any subject who receives at least 1 dose of study drug.

The efficacy analysis set will include any subject who receives at least 1 dose of study drug and at least one post-dose cognitive assessment.

Analyses will be fully outlined in a Statistical Analysis Plan finalized prior to the end of enrollment.

8.4. Safety

The incidence of treatment-emergent AE and SAEs, the causal relationship between an AE/SAE, and the Study Drug and severity will be tabulated by treatment (dose) group.

Individual clinically-significant changes in clinical laboratory and ECG parameters will be listed along with median and mean and standard deviation by treatment group.

8.5. Efficacy

The primary efficacy variable is:

Change in the composite score of the NTB, including assessments of attention, executive
function, and visuospatial function in neflamapimod treated-subjects as compared to the
placebo-treated subjects.

Secondary efficacy variables are:

- Change in CDR-SB in neflamapimod-treated subjects compared to placebo-recipients.
- Change in MMSE in neflamapimod-treated subjects compared to placebo-recipients.
- Change in NPI-10 domains in neflamapimod-treated subjects compared to placeborecipients.
- Change in ISLT in neflamapimod-treated subjects compared to placebo-recipients.
- Change in Timed Up and Go Test.
- Change in EEG parameters.

The estimand of this study is the change from baseline to Week 16 in the composite score of the NTB in patients 55 years of age and older with probable DLB, comparing subjects treated with neflamapimod to those treated with placebo. The NTB includes assessments of episodic memory, executive function, visuospatial function, and attention. The primary endpoint will be analyzed using the Mixed Model Repeated Measures (MMRM) analysis method with the NTB change from baseline composite score as the dependent variable, and will use an unstructured covariance matrix. This analysis will be performed on the efficacy analysis population, which will include all subjects who receive at least one dose of study drug and provide at least one post-dose cognitive assessment. Additional covariates to be included in the MMRM model will be provided in the Statistical Analysis Plan (SAP) which will be finalized prior to study unblinding. Z-scores may be calculated and used in order to create standardized change scores to be used for the analysis. Additionally, sensitivity analyses will be performed on the primary endpoint specifically to address different missing data scenarios, both Missing at Random and Missing Not at Random. Further descriptions of the sensitivity analyses, as well as any additional efficacy populations that may be used to assess efficacy will also be provided in the SAP. Secondary efficacy endpoints will utilize the same analysis method and model as the primary endpoint.

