	The secondary objectives are to:		
	Evaluate the effects of neflamapimod on informant/caretaker evaluation of cognition and function, as assessed by the Clinical Dementia Rating Scale-Sum of Boxes (CDR-SB).		
	Assess the effects of neflamapimod on general cognition, as assessed by the Mini Mental State Examination (MMSE).		
	Assess the effects of neflamapimod on episodic memory, as assessed by the International Shopping List Test (ISLT).		
	 Assess the effects of neflamapimod on select domains of the 10-item Neuropsychiatric Inventory (NPI-10), including depression (dysphoria), anxiety, hallucinations, and agitation/aggression. 		
	 Evaluate the effects of neflamapimod on motor function as assessed by the Timed Up and Go Test (TUG). 		
	• Evaluate the effects of neflamapimod on quantitative electroencephalography (EEG) parameters.		

Study Endpoints	Primary endpoints:		
	Change in the composite score of the NTB, including assessments of attention, executive function, and visuospatial function in neflamapimod treated-subjects as compared to the placebo-treated subjects.		
	Secondary endpoints:		
	Change in CDR-SB in neflamapimod-treated subjects compared to placebo- recipients.		
	 Change in MMSE in neflamapimod-treated subjects compared to placebo- recipients. 		
	Change in NPI-10 domains in neflamapimod-treated subjects compared to placebo-recipients.		
	Change in International Shopping List Test immediate & delayed recall and recognition in neflamapimod-treated subjects compared to placebo-recipients.		
	Change in Timed Up and Go Test.		
	Change in EEG parameters.		
Number of Subjects	80 subjects are planned to be enrolled		
Subject Population	Subjects aged ≥55 years with mild-to-moderate (MMSE 15-28) probable DLB by consensus criteria (McKeith et al, 2017), including a positive DaTscan TM , who are currently receiving cholinesterase inhibitor therapy. If the DaTscan is negative, but the subject has historical polysomnography (PSG)-verified REM sleep behavioral disorder (RBD), this will also qualify as probable DLB.		
Inclusion Criteria	1. Men and women aged ≥55 years.		
	2. Subject or subject's legally authorized representative is willing and able to provide written informed consent.		

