Neflamapimod has not been evaluated previously in DLB. However, though patients present with a broader set of cognitive deficits (e.g., visual-spatial deficits), episodic memory deficits attributable to hippocampal dysfunction are prominent, though generally considered qualitatively different from that in in AD (Park, et al 2011; Galvin, 2015; Adamowitz et al, 2017). As a result, based on the prior rationale for p38α kinase inhibition to address hippocampal dysfunction as well the preliminary clinical evidence with neflamapimod in patients with AD, neflamapimod could be expected to improve episodic memory in patients with DLB.

In addition, based on the potential to impact broadly the disease pathogenesis of DLB, neflamapimod might be expected to impact synaptic dysfunction regions outside the hippocampus as well. For example, with respect to underlying disease pathogenesis, based on genetic evaluation, DLB appears to be overlapping with disease pathogenesis for both AD and PD (Guerreiro et al, 2016). Apoliprotein E (APOE) genotype variants are associated with both DLB and AD, while the major biologic impact of the disease-associated APOE4 variant is to augment the neuroinflammatory response (Keene et al, 2011). As such, inflammation-induced synaptic dysfunction, regardless of the brain region impacted, is likely to be drivers of disease in both settings; a concept that is supported by the finding of elevated markers of inflammation in the brain of both disorders (Mrak and Griffin, 2007). With respect to disease pathogenic mechanisms that are common to DLB and PD, the most important is considered to be the neurotoxicity of α-synuclein, the constituent of "Lewy bodies" that is the major pathologic correlate of both diseases. Importantly, p38 kinase has been linked to the neurotoxicity of α-synuclein in a range of in vitro and invivo model systems (Obergasteiger, et al, 2018; Chen et al, 2018).

The primary objective of this study is to assess the impact of neflamapimod on cognitive function domains (attention, executive function, visuospatial function) that depend on proper synaptic function in the frontal and parieto-occipital regions of the brain. A secondary objective is to evaluate the effects of neflamapimod on episodic memory function, which depends primarily on hippocampal synaptic function.

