2.2. Secondary Objectives

The secondary objectives are to:

- Evaluate the effects of neflamapimod on informant/caretaker evaluation of cognition and function, as assessed by the Clinical Dementia Rating Scale-Sum of Boxes (CDR-SB)
- Assess the effects of neflamapimod on general cognition, as assessed by the Mini Mental State Examination (MMSE)
- Assess the effects of neflamapimod on episodic memory, as assessed by the International Shopping List Test (ISLT).
- Assess the effects of neflamapimod on select domains of the 10-item Neuropsychiatric Inventory (NPI-10), including depression (dysphoria), anxiety, hallucinations, and agitation/aggression.
- Evaluate the effects of neflamapimod on motor function as assessed by the Timed Up and Go Test (TUG).
- Evaluate the effects of neflamapimod on quantitative electroencephalography (EEG) parameters.

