3.1.2. Treatment Period

Once eligibility is confirmed during the Screening period and before the first dose of study drug, subjects will be randomly assigned on a 1:1 basis to placebo or neflamapimod for the 16-week treatment period. Investigators and subjects will be blinded to the treatment assignment. Randomization will be stratified by ISLT Total Recall score at Baseline ($\leq 21 \text{ vs.} > 21$), i.e. by wheter patients have an episodic memory defect at baseline or not.

Subjects will receive study drug for 16 weeks. Dosing will start on Day 1 following completion of all baseline procedures. During the 16-week treatment period, subjects will return to the clinic every 2 weeks for the first month and then every 4 weeks thereafter. A Follow-Up will be conducted 2 weeks (±3 days) after completion of study drug or after the Early Termination visit.

The NTB, ISLT, and NPI-10 will be conducted at Screening, Baseline (Day 1), Week 4 (Day 28), Week 8 (Day 56), and Week 16 (Day 112) or ET if early termination. The CDR-SB and TUG will be conducted at Baseline (Day 1), Week 8 (Day 56), and Week 16 (Day 112) or ET. The MMSE will be conducted at Screening, Baseline (Day 1), Week 8 (Day 56), and Week 16 (Day 112) or ET. EEGs will be conducted at Baseline (Day 1) and Week 16 (Day 112) or ET. Samples for plasma biomarkers will be obtained at Screening, Baseline (Day 1) and Week 16 (Day 112).

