6.2.4. Cognitive Function Tests

Cognitive function tests include a Neuropsychological Test Battery (NTB) as well as the Letter Fluency Test and Category Fluency Test (CFT), which are all components of the primary objective/endpoint to assess attention, executive function, and visuospatial function.

Cognitive function tests to be performed as components of the secondary objective include the CDR-SB, MMSE, NPI-10, Timed Up and Go (TUG), and International Shopping List Test (ISLT).

At Baseline and on any visits at which both NTB and other cognitive tests are conducted, the NTB should be performed prior to the other tests.

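### Does naming episodic memory in the Section 8.5 estimand paragraph change what the primary NTB composite contains?

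*Protocol*

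**What the plan says.** Section 8.5 describes the Neuropsychological Test Battery (NTB) twice. The primary efficacy variable is the change in the NTB composite, worded as in the synopsis: "including assessments of attention, executive function, and visuospatial function in neflamapimod treated-subjects". The estimand paragraph further down the same section adds a fourth domain: "The NTB includes assessments of episodic memory, executive function, visuospatial function, and attention".

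Two other sections bear on the domains:

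- Section 1.1 ties the primary objective to "cognitive function domains (attention, executive function, visuospatial function) that depend on proper synaptic function" in frontal and parieto-occipital regions. It then sets memory apart: "A secondary objective is to evaluate the effects of neflamapimod on episodic memory function".
- Section 6.2.4 says of the battery and the two fluency tests: "which are all components of the primary objective/endpoint to assess attention, executive function, and visuospatial function". It places the ISLT among the tests for the secondary objective.

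Section 2.2 assigns episodic memory to the ISLT, and Section 8.5 lists change in ISLT as a secondary efficacy variable.

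The tests themselves are listed in the synopsis, Section 2.1 and Section 6.2.4.1. They are Cogstate Detection, Identification, One Card Learning and One Back, plus Letter Fluency and Category Fluency.

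**The concern.** The odd sentence sits in the paragraph that defines the estimand and the dependent variable of the mixed model for repeated measures (MMRM). Wording about the primary endpoint should be unambiguous there.

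Memory is also not an incidental word in this programme. Sections 1.1 and 3.2.1.1 rest the clinical rationale on improved episodic memory in early Alzheimer's disease, and Section 1.1 expects the drug might improve episodic memory in dementia with Lewy bodies. Keeping memory out of the primary endpoint therefore looks deliberate, and a sentence that puts it back in looks like a conflict of substance.

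Two consequences could be feared:

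- Someone might cite the sentence to bring the ISLT into the primary composite, so that one measure counted as both primary and secondary. The ISLT is collected at the same visits as the NTB, and Section 8.5 leaves the use of z-scores open, so this would be easy to do.
- A result on the composite might be reported as evidence of a memory effect.

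**Working it through.** The protocol makes no formal sample size calculation (Section 8.2), so there is no planned figure to reproduce. The check is a comparison of texts.

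**Step 1: domains named for the primary endpoint.**

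| Place | Domains | Episodic memory included? |
|---|---|---|
| Synopsis, Study Endpoints | 3, introduced by an open word | no |
| Section 1.1 | 3, in parentheses | no, set apart as secondary |
| Section 6.2.4 | 3 | no |
| Section 8.5, primary efficacy variable | 3, introduced by an open word | no |
| Section 8.5, estimand paragraph | 4 | yes |

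In the synopsis and in the primary efficacy variable the list is introduced by a word that does not close it. Read alone, the two sentences of Section 8.5 can both be true. The firm disagreement is between the estimand sentence and Sections 1.1 and 6.2.4. It is not strictly inside Section 8.5.

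**Step 2: tests named for the NTB.**

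| Place | Tests | ISLT included? |
|---|---|---|
| Synopsis, Study Objective | 6 | no |
| Section 2.1 | the same 6 | no |
| Section 6.2.4.1 | the same 6 | no |

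**Step 3: where the ISLT appears.** Section 3.1.2 and Table 6-1 name it next to the NTB as a separate item. Sections 2.2, 6.2.4 and 8.5 class it as secondary. Sections 3.1.2, 3.2 and 5.4 use its baseline total recall as the stratification factor. Nowhere is it called part of the NTB.

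**Step 4: which definition governs.** The estimand and the MMRM dependent variable are both the NTB composite score. A composite is computed from test scores, not from domain labels. The test list is closed and identical in all three places, so the computed variable is the same under either label list.

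**Step 5: what the extra label could mean.** The protocol assigns none of the six tests individually to one of the four domains. Two readings are possible:

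- *A label for one of the six tests*, for example One Card Learning. With equal weights (an assumption) that test already carries 1/6 = 17% of the composite. Nothing changes.
- *An instruction to add the ISLT.* With equal weights, one ISLT score would carry 1/(6+1) = 14%. All three scores (immediate recall, delayed recall, recognition) would carry 3/(6+3) = 33%. That would change the endpoint, but Steps 2 and 3 rule this reading out.

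Any loss of power belongs to the second reading only. It would also depend on inter-test correlations and effect sizes that the protocol does not give, so it does not measure anything in the plan as written.

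**Step 6: the related wording in Section 6.2.4.** That section mentions the NTB and then the two fluency tests as if they were additional, while Section 6.2.4.1 lists them inside the NTB. The same sentence of Section 6.2.4 makes all of them components of the primary endpoint, so the set of tests is again six.

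**The case for a change.** The best case for a correction is that this is an inaccurate statement in the protocol itself, not a detail left to the statistical analysis plan. A plan that follows three domains disagrees with the estimand sentence; one that follows four disagrees with Sections 1.1 and 6.2.4. The open word in the primary variable does not fully rescue the text, because Section 1.1 names the three primary domains and expressly separates memory as hippocampal and secondary. The only test the protocol ties to episodic memory by name is the ISLT. Correcting the words would cost almost nothing.

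Much of this stands. The labels do disagree, and a reader cannot tell from the protocol what the fourth label refers to. What does not stand is the step from a loose label to a different endpoint. Using the sentence to admit the ISLT would mean overriding a test list given three times and a secondary classification given in the same section. Section 8.5 also requires the statistical analysis plan to be final before unblinding, so the components can be restated under the blind.

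The obvious correction is not secure either. If one of the six tests does measure memory, deleting the words would make the description less accurate. As for over-claiming a memory effect, the composite's six-test make-up and the separately reported ISLT would show that whatever this sentence says.

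**Conclusion.** The mismatch is real but editorial: four domain labels in one sentence against three elsewhere, with six identical tests in every list. The primary variable, population, time point and model do not depend on which labels are read, so the effect on the primary analysis is zero and no change to the plan is needed.

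This rests on one assumption: that the analyst builds the composite from the tests listed in Sections 2.1 and 6.2.4.1 and keeps the ISLT as secondary. The protocol directs exactly that, and no part of it directs otherwise. A change of label would not alter any result, and the protocol does not show which label list is the accurate one.
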